4.3 Participant Registration

[figure not shown]
Study registration will occur after the informed consent process is completed, consent form is signed and screening eligibility is confirmed. No study procedures will be conducted until after the consent form is signed, either electronically or a paper copy mailed or faxed to the clinic. To be enrolled in this study following screening, the participant must meet each criterion listed on the eligibility checklist based on the eligibility assessment documented in the case report record. Upon completion of the screening evaluation, and confirmation of eligibility, the study coordinator or designee will enroll the subject into REDCap.

5 Experimental Design:

Smokers will undergo a screening and then a three phase, 9 week experimental trial (Figure 1) with a one month follow-up at Week 10:

- 1) Phase 1 – Usual Brand Baseline: 1 week baseline assessment period of usual brand cigarette smoking;
- 2) Phase 2 – Study Cigarette Adaptation & Baseline Period: 2 week period allows the subject to adjust to the ventilated study cigarettes and obtain baseline data prior to randomization;
- 3) Phase 3 – Intervention: Randomization to either ventilated or unventilated study cigarettes for 6 weeks.

Figure 1:

[figure not shown]

Design

Subjects will be randomized at the end of Phase 2 (Visit 00) to one of the two experimental conditions (ventilated vs. unventilated cigarettes) for the 6-week intervention. An intervention

of six weeks was chosen because compensation is likely to stabilize by two weeks and biomarker levels should stabilize by six weeks.^{12,13}

Figure 2. Intervention Groups

Subjects will be informed of their assignment to ventilated cigarettes (cigarettes with similar ventilation as their usual brand) or unventilated cigarettes. As described above, study cigarettes are provided under single-blind conditions where subjects will not be informed of the filter design of the study cigarettes.

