WISDM: **Wisconsin Inventory of Smoking Dependence Motives (Brief)**: a 37 item questionnaire to measure tobacco dependence by measuring a variety of smoking motives.

Study Synopsis

Study Design:	This single-blind, between-subject, randomized, multi-center study will assess the effect of cigarettes with unventilated vs. ventilated filters on smoking behavior and biomarkers of tobacco toxicant exposure. The study uses telehealth and brief in-clinic or curbside visits and will also examine the feasibility of remote collection of multiple biological samples. Subjective measures, alveolar carbon monoxide, blood pressure and cigarettes per day will be collected remotely. Biological samples collected at home will be dropped off at the clinic during a brief clinic or curbside visit where the study cigarettes will be dispensed.
Primary Aim:	To examine the effects of unventilated vs ventilated filter cigarettes on urinary biomarkers of toxicant exposure and smoking behavior (e.g., cigarettes per day, intensity of smoking).
Secondary Aim	To examine the effect of unventilated vs. ventilated filter cigarettes on cigarette dependence and subjective responses to cigarettes (e.g., perceptions of harm).
Exploratory Aim	To examine how the biomarkers analysis collected via different biological samples are concordant.
Population:	Cigarette smokers
Study Procedures:	Smokers using conventional cigarette brands with filter ventilation of about 16-36% will enter a three phase study. Phase 1 is a 1-week baseline period of smoking usual brand cigarettes; Phase 2 consists of 2 weeks of smoking ventilated study cigarettes; and Phase 3 where subjects are randomly assigned to one of two conditions: 1) ventilated cigarettes; or 2) unventilated cigarettes smoked for a 6 week period. Weekly telehealth visits are conducted to collect study measures and subjects attend a brief clinic or curbside visit to pick up study cigarettes and drop off biomarker samples. A follow-up telehealth visit will occur at one-month post intervention.
Accrual Goal:	162 (81 per group) enrolled
Enrollment Period	May 2021 – December 2022

1 Study Objectives and Hypotheses

The goals of this project are to determine the effects of varying degrees of cigarette filter ventilation on biomarkers of toxicant exposure and smoking behavior and on subjective responses to the cigarette.

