Developing the science to determine if filter ventilation should be banned. The 2014 SGR stated that, "if the risk of lung cancer has increased with changes in the design and composition of the cigarettes, then the potential exists to reverse the risk through changes in design and composition (p. 186)." The report went on to say that "even a modest reduction in the large burden of mortality from lung cancer would result in saving a substantial number of lives over time (p. 186)." This study will use a systematic and comprehensive effort to examine one type of design feature, based on extensive review of the literature that may have led to the increase in lung cancer deaths, in particular adenocarcinoma lung cancer. Independent of the effects of ventilated cigarettes on lung adenocarcinoma, removing filter ventilation has the potential to reduce misperceptions regarding the relative harm of these cigarettes. We begin with the premise that ventilated cigarettes should be regulated, and herein we study its complete removal. This proposed study complements other studies conducted by our research team examining the effects of cigarette ventilation levels on biomarkers from lung bronchoscopies and particle distribution in the lungs. The aim of this study will be to examine the impact of ventilated vs. unventilated cigarettes on several biomarkers of specific exposures and effects (assessed via urine, saliva, oral cells and potentially hair and blood and inhalation measures), and examining smoking topography via spent filter analysis while holding levels of TSNAs constant. The overarching goal is to make sure that a proposal to ban filter ventilation does not lead to greater toxicant exposure, dependence and thereby potential harm, complementing other program project studies that examine misperceptions of ventilated cigarettes and potentially greater harm by examining the effects of these cigarettes in the lung.

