Note: The original NIH funded study design involved in person contact with the participants. This study was approved by the IRB (STUDY 00003531). Since the COVID-19 pandemic, we have limited our in-person contact while conducting human clinical trials that do not have a direct therapeutic benefit to the participant. Because it is unknown when we will be able to conduct the originally designed trial again and the uncertainty regarding the course of the pandemic, we have adapted this original study to be conducted primarily remotely, with a brief clinic or curbside component to drop off biosamples and pick up study cigarettes. The recent improvements in controlling the COVID-19 virus

has allowed us to conduct some of our measures face-to-face. As the situation continues to improve, we propose to resume the inhalation measures on a subset of study participants.

3 Summary

The **primary aim** of this study is to examine the effects of unventilated vs. ventilated filter cigarettes on an exposure biomarker of a potent lung carcinogen and smoking behaviors (e.g., cigarettes per day, filter analysis).

A **secondary aim** includes determining the effects of unventilated vs. ventilated filter cigarettes on cigarette dependence and subjective response to cigarettes.

Study Design

This is a randomized, single-blind, multi-site study where subjects (N=162; 81 in each group) are randomly assigned to one of two cigarettes with different filter designs: 1) Ventilated cigarettes; or 2) Unventilated cigarettes.

4 Subject Selection

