5.6 Phase 2: Adaptation to Ventilated Study Cigarette

During Phase 2 (baseline 92 to randomization visit 00), eligible subjects will be provided study ventilated cigarettes. Subjects will be instructed to continue to report on daily intake of tobacco and nicotine products, alcohol and marijuana in the ITR. Data will be collected during telehealth visits and biological samples for biomarker analysis collected at the brief clinic or curbside visit.

Procedures for Visit Telehealth Visit (Visit 91)

A. Physiological Measures:

- 1) CO level will be measured while conducting the telehealth visit.
- 2) Vitals signs (blood pressure, heart rate) will be obtained while conducting the telehealth visit.

B. Surveys – link sent to participant to complete REDCap based survey:

Subjective Outcome Measures:

- 1) Minnesota Nicotine Withdrawal Scale(MNWS)
- 2) Questionnaire of Smoking Urges-brief scale - Study Cigarette (QSU)
- 3) Modified Cigarette Evaluation Scale – Study Cigarettes
- 4) Respiratory Symptoms and Global Health Questionnaire
- 5) Duke Sensory Questionnaire – Study Cigarettes
- 6) BDI-II and or GAD7 will be administered for clinician to review if monitored for depression or anxiety.

C. Interviews - Research Assistant interviews participant and enters directly into REDCap:

- 1) COVID-19 Assessment
- 2) Health Changes and Menstrual Cycle Questionnaire
- 3) Adverse Events
- 4) Concomitant Medications
- 5) Daily IVR Call Review (follow-up on missing and unusual reports)
- 6) Timeline Follow Back Questionnaire
- 7) Intention to Quit
- 8) Drug accountability: Complete Dispensing Logs
- 9) Compliance Review
- 10) End of Visit Evaluation.

Supplies, sample collection containers and handouts will be provided to the participant at the Baseline 91 brief clinic or curbside visit for collection of cigarette butts, urine, saliva and blood spots for the Week 0 baseline sample collection. Participants will be asked to collect cigarette butts 24 hours prior to Visit 00.

Procedures for Visit 2 Telehealth Visit (Visit 00)

At the second Baseline visit (00), subjects will be informed that they have been randomized to either ventilated or unventilated study cigarettes. Subjects will complete several measures and provide biological samples for biomarker analysis as described below.

A. Physiological Measures and Biomarker Samples:

- 1) Vitals signs (blood pressure, heart rate) will be obtained while conducting the telehealth visit.

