- 2) Carbon monoxide level will be obtained while conducting the telehealth visit.
- 3) Biological sample collection for analysis of nicotine and carcinogen metabolites will be collected prior to (first void urine sample) or at the telehealth visit (saliva and possibly blood spots) and then dropped off at the brief clinic or curbside visit. Oral cells will be collected during the telehealth, in-person curbside or clinic visit. Subjects will be instructed to brush teeth prior to the collection.
- 4) Review Cigarette Butt Collection: The 24-hour collection of cigarette butts prior to this visit will be reviewed and dropped off at brief clinic or curbside visit. These spent filters will be analyzed for cigarette butt staining to inform intensity of smoking behavior.

B. Surveys – link sent to participant to complete REDCap based survey:

Biomarker Modifier Questionnaires:

- 1) Environmental Tobacco Smoke Questionnaire

Subjective Outcome Measures:

- 1) Minnesota Nicotine Withdrawal Scale(MWSC)
- 2) Questionnaire of Smoking Urges-Brief Scale – Study Cigarette (QSU)
- 3) Respiratory Symptoms and Global Health Questionnaire
- 4) Modified Cigarette Evaluation Scale – Study Cigarette
- 5) Perceived Health Risk
- 6) Cigarette Purchase Task – Study Cigarette
- 7) Nicotine Dependence Questionnaire
- 8) Duke Sensory Questionnaire – Study Cigarette
- 9) BDI-II and or GAD7 will be administered for clinician to review if monitored for depression or anxiety.

C. Interviews - Research Assistant interviews participant and enters directly into REDCap:

- 1) COVID-19 Assessment
- 2) Health Changes and Menstrual Cycle Questionnaire
- 3) Adverse Events
- 4) Concomitant Medications
- 5) Daily ITR Review (follow-up on missing and unusual reports)
- 6) Timeline Follow-back Questionnaire (since last visit)

- 7) Randomization to either ventilated or unventilated cigarettes - Read appropriate script
- 8) Intention to Quit
- 9) Product Accountability Log
- 10) Compliance Review
- 11) End of Visit Evaluation

Dispensing Study Product:

At the brief clinic or curbside visit, the participant will be provided their randomized study cigarettes (ventilated or unventilated). The subject will continue to be allocated 150% of their baseline cigarettes per day and receive a \$2 credit per pack for each unused pack of cigarettes that are returned in order to disincentivize wasteful use of cigarettes (sharing with friends, hoarding cigarettes; max credit up to \$30).

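### Section 5 says both that subjects are told their assigned cigarette and that they are not told its filter design, so the visible documents leave the single-blind status unresolved

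*Combined protocol and SAP*

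**What the plan says.** Section 5 (Experimental Design), in the text beside Figure 2, has two adjacent sentences on what subjects learn. The first is: "Subjects will be informed of their assignment to ventilated cigarettes (cigarettes with similar ventilation as their usual brand) or unventilated cigarettes". The second, which refers back to an earlier description, says that "study cigarettes are provided under single-blind conditions where subjects will not be informed of the filter design of the study cigarettes".

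The design label appears in two other places. The Study Synopsis opens with "This single-blind, between-subject, randomized, multi-center study will assess the effect of cigarettes with unventilated vs. ventilated filters", and section 3 (Summary, Study Design) states: "This is a randomized, single-blind, multi-site study". Neither says who is blinded.

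The operational text is in section 5.6, under the visit 00 procedures. The narrative says that at this visit "subjects will be informed that they have been randomized to either ventilated or unventilated study cigarettes". Item 7 of the interview list reads "Randomization to either ventilated or unventilated cigarettes - Read appropriate script".

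**The concern.** Site staff have one instruction to disclose the arm and, in the next sentence, one to withhold it. Whichever they follow, section 5 misdescribes the trial.

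This matters because several endpoints are what subjects report. Section 10.1 makes cigarettes per day (CPD), taken from subjects' own daily reports, a primary endpoint. It makes the Fagerström score (FTND), the modified Cigarette Evaluation Scale (mCES) and Perceived Health Risk secondary endpoints. Section 1.2 predicts that the arms will differ in perceived harm, and section 2 gives smokers' beliefs about ventilated cigarettes as a reason for the research. If subjects are told which type they hold, the arm contrast in these measures could combine the effect of smoking the product with the effect of hearing its name. A reader who takes the trial to be single-blind would attribute all of it to the product.

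**Working it through.** No arithmetic applies: the point depends on no margin, power or sample size. The check is to set side by side every visible statement on blinding or disclosure.

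1. **Can both sentences in section 5 be followed?** That depends on what filter design means. Section 3 says subjects are "randomly assigned to one of two cigarettes with different filter designs: 1) Ventilated cigarettes; or 2) Unventilated cigarettes". There, the filter designs are the arms. Section 5.1 says the tobacco blend, additives, nicotine and tar are the same in both cigarettes and that they differ in the degree of ventilation. On that description, naming the arm names the filter design, so on the natural reading the two sentences exclude each other.

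2. **Does the earlier text decide it?** The second sentence in section 5 points back to an earlier description. The earlier places that address blinding are the synopsis and section 3, and both give only the label. The second sentence is the only visible statement that it is the subjects who are blinded, and it is itself one side of the conflict.

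3. **Does the visit 00 narrative decide it?** It can mean that each subject is told which of the two cigarettes was assigned, or only that assignment to one of the two has taken place. Either reading fits the words.

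4. **Does the interview list decide it?** A script described as appropriate, attached to a choice between two arms, suggests a different script for each arm. That leans towards disclosure. The script's wording is not in the documents, so it is not conclusive.

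5. **Which endpoints could be touched if the arm is disclosed?** Perceived Health Risk, mCES, FTND and self-reported CPD could respond directly to the label. NNAL, the other biomarkers, the spent-filter analysis and the inhalation measures are assayed or instrument-based. A label could reach them only by changing how people smoke.

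Result: one sentence directs disclosure, the sentence after it directs non-disclosure, two labels do not say who is blinded, one procedure is ambiguous and one leans towards disclosure. No visible passage says which governs.

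**The case against.** **The deciding text may lie elsewhere.** What subjects hear is carried by the visit 00 script, the orientation presentation (section 5.4) and the consent form (section 11). Figure 2 and the consent pages are absent from the text available for review, which is not a fault in the plan. This stands as a limit: the finding concerns the visible wording. It does not remove a contradiction between two current sentences of the protocol.

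**Filter design could mean technical detail.** Section 5.1 gives vent number and percentage ventilation separately from the arm names, and section 2 mentions the design of filter material apart from ventilation. Subjects might be told the arm but not the specification. This is possible, but section 3 makes it the weaker reading. Even then, subjects would know their arm, and single-blind would not describe the contrast being tested.

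**Disclosure may be intended and legitimate.** Section 2 describes the main purpose of the work as follows: "make sure that a proposal to ban filter ventilation does not lead to greater toxicant exposure, dependence and thereby potential harm". A ban would be a known product change, so a known-product comparison could suit that question. This stands, but the plan would then have to say so and stop calling the trial single-blind.

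**CPD is checked and NNAL is assayed.** Section 5.15 compares daily texts, Timeline Follow-back and accountability logs with photographs. Empty packs and 24-hour butt collections are also returned. These limit misreporting. They do not remove a real change in smoking in response to a label. It is fair that NNAL, which set the sample size, is only indirectly exposed.

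**Stronger readings that the documents do not support.** A reader might infer that subjects are in fact unblinded; the visible text does not establish this. A reader might also infer that adjusting for visit 00 cannot help, because section 5.6 lists the surveys before the script. The lists are grouped by type of measure, however, and section 11 (Data Integrity) says a visit checklist sets the order of administration. Finally, a reader might infer that the CPD non-inferiority test has an inflated error rate. Quantifying that would need a label effect and a planning difference, and the documents give neither.

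**Conclusion.** The point holds as a contradiction in the wording of section 5 that the rest of the visible text does not resolve. That rests on reading filter design as the arm, which section 3 supports and section 5.1 reinforces.

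The consequence is conditional. If the disclosure sentence is followed, the single-blind description is false, and the contrasts in Perceived Health Risk, mCES, FTND and CPD could include a label effect of unknown size and direction. If the non-disclosure sentence is followed, the label is accurate and the disclosure sentence is the error. No numerical size can be given from the documents. The plan should be corrected because a primary endpoint is self-reported, a difference in perceived harm is a stated hypothesis, and the correction costs very little.

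**What to change.** Reconcile the synopsis, section 3, section 5 and the visit 00 procedures in section 5.6 so that they say the same thing about what subjects are told and who is blinded. Align the visit 00 script with them. There are two coherent choices.

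- **(a) Keep the trial single-blind.** Delete the sentence in section 5 saying that subjects learn their assignment. Use one identical, neutral script in both arms. Keep what subjects are told about the Phase 2 study cigarette consistent with that, since a subject who knows that cigarette was ventilated has a reference for comparison. Disclose the filter type only after the last questionnaire at Week 6 or early termination.
- **(b) Disclose the arm.** Remove single-blind wherever it appears, together with the non-disclosure sentence. State that the perception, satisfaction, dependence and CPD contrasts reflect product plus label.

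Either choice costs only protocol and script wording: no added visits, samples or subjects. Option (a) has a limit. It removes an avoidable label but does not stop subjects noticing the switch after two weeks on ventilated cigarettes. Section 7 itself lists throat irritation and more cough as possible effects of the unventilated product.

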5.1 Investigational Tobacco Products

Tobacco Products:

Study Cigarettes: The study cigarettes will be a conventional manufactured cigarettes (e.g., Pyramid 100 mm). The investigational cigarettes are either: 1) ventilated (e.g., 28% +/- 4% filter ventilation); or 2) unventilated (e.g., ~0-5% filter ventilation). Product characteristics including blend of tobacco, additives, nicotine and tar content levels will be identical across these two cigarettes but will differ in the degree of ventilation (number of filter vents), e.g., no ventilation or ventilation (the extent of ventilation found in former “light” to “ultra-light” cigarettes). The dose of nicotine will be similar to usual brand cigarettes. The tobacco will be tested periodically to verify constituent levels are stable.

At each visit, the subject will receive 150% of their baseline cigarettes per day. Providing additional cigarettes per day will allow for potential compensatory smoking or a potential delay in attending the brief clinic or curbside appointments. Menthol and non-menthol cigarettes will be provided, as preferred.

5.2 Assessing Smoking Behavior

Smoking inhalation measures will be performed at visits 00 & 6 on a subset of subjects. The device provides valid and widely used objective measures of inhalation. Inhalation: Inductance plethysmography will be done using the BioRadio Wireless Physiology Monitor (<https://glneurotech.com/bioradio/>) analyzed by the VivoSense Complex Respiration Analysis software (<http://vivonoetics.com/products/vivosense/>). This is a dual band device that is placed over the upper chest and abdomen that records respiration as a continuous stream to memory for download and analysis. The data is analyzed for metrics such as tidal volume, inspiratory volume and time, expiratory volume and time, and flow-volume loops. This system has been validated

and is widely used for focusing on respiratory disease. The spent cigarette filter (cigarette butt) from the session will be collected.

Study Procedures

5.3 Telehealth Visit Scheduling Requirements:

Scheduling window for Phase 1 usual brand baseline screening (93) to baseline (92) visit is 7 days (+ 7 days). If the subject is unable to schedule within 30 days, they will be re-consented, but will maintain the original assigned Subject Identifier.

Scheduling window for Phase 2 weekly adaptation visits (92) to randomization (00) visits is 7 days (+4) days.

Scheduling window for Phase 3 weekly visits for Week 1-6 is 7 days (-3/+4) days. Follow-up (Week 10) scheduling window is 70 days from Week 00 visit (-3/+21).

